- 16. Any of the following chronic, severe conditions or treatments that may impact the compliance of the study:
 - History of, or current, significant cardiac disease including cardiac failure (NYHA functional class II-IV), myocardial infarction (within 6 months prior to screening), unstable angina (within 6 months prior to screening), transient ischemic attack (within 6 months prior to screening), stroke, cardiac arrhythmias requiring treatment or uncontrolled arterial hypertension
 - Concomitant clinically significant cardiac arrhythmias, e.g. sustained ventricular tachycardia and clinically significant second or third degree AV block without a pacemaker on screening electrocardiogram (ECG)
 - History of or active severe respiratory disease, including Chronic Obstructive Pulmonary Disease, interstitial lung disease or pulmonary fibrosis
 - Subjects with asthma requiring regular treatment with oral steroids
 - Severe hepatic impairment (Child-Pugh class C) or any chronic liver or biliary disease

- Subjects with severe renal impairment (Glomerular Filtration Rate < 30 ml/min/ 1.73 m^2
- Any medically unstable condition as determined by the Investigator
- severe hypoproteinaemia e.g. in nephrotic syndrome
- 17. Any of the following abnormal laboratory values as confirmed by the central laboratory prior to first study drug administration:
 - Lymphocyte count $<500/\text{mm}^3$ ($<0.5 \times 10^9/\text{L}$) in patients discontinuing fumarates
 - Serum IgG < 500 mg/dL (according to central laboratory range)
 - Any other clinically significant laboratory assessment as determined by the Investigator (e.g. significant anemia, neutropenia, thrombocytopenia, signs of impaired bone marrow function)
- 18. Subjects with any of the following neurologic/psychiatric disorders prior to first study drug administration:
 - Score "yes" on item 4 or item 5 of the Suicidal Ideation section of the Columbia-Suicide Severity Rating Scale (C-SSRS), if this ideation occurred in the past 6 months, or "yes" on any item of the Suicidal Behavior section, except for the "Non-Suicidal Self-Injurious Behavior" (item also included in the Suicidal Behavior section), if this behavior occurred in the past 2 years.
- 19. History of hypersensitivity to the study drug or any of the excipients or to drugs of similar chemical classes

6 **Treatment**

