9.2.1 Safety Follow-up

Subjects moving into the Safety Follow-up period, as described in Section 3, will continue for 6 months post last dose of ofatumumab treatment. A shorter follow-up time is acceptable if subjects select a different MS treatment during this period as presented below.

At the EOS + M6 Visit:

- If a subject has IgG and IgM results ≥ screening or LLN, this visit shall be considered final clinic visit for the subject. The End of Safety Follow-up visit will be performed by telephone contact to inform the subject that his or her participation in Safety Follow-up has ended; the disposition form will be completed at that time and the AE and concomitant medications eCRF will be updated if necessary to record any new or worsening events or medication changes since the last clinic visit.
- If a subject has either IgG or IgM results < screening or LLN, Safety Follow-up clinic visits will continue on a plus 3 monthly basis until both IgG and IgM values are ≥ screening or LLN. The End of Safety Follow-up visit will be performed by telephone contact to inform the subject that his or her participation in Safety Follow-up has ended; the disposition form will be completed at that time and the AE and concomitant medications eCRFs will be updated if necessary to record any new or worsening events or medication changes since the last clinic visit; refer to Table 8-2.

• Note: All IgG and IgM results are required to be confirmed by a Central Laboratory result. IgG/IgM assessments performed by a local laboratory under the Public Health Emergency mitigation procedures defined in Section 8.4.5 are not to be used to determine if the subject has met the criterion for their last immunoglobulin follow-up visit. During a Public Health Emergency, subjects should continue to be monitored until it is feasible and safe to schedule a clinic visit to obtain a sample for central laboratory evaluation unless Last Subject Last Visit (LSLV) has already been declared for the study. In such circumstances, please follow the guidance presented below.

Patients starting a different MS treatment during Safety Follow-up:

• During Safety Follow-up subjects may receive any DMT for the treatment of MS as the investigator deems necessary. Prior to starting the MS DMT, subjects will be brought in for their final Safety Follow-up visit. This visit will be the End of Safety Follow-up visit for the subject and the disposition page will be completed at this time.

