2.9.3.1 Other special lab results

Other non-routine laboratory data include B-cell counts, total IgG, total IgM, and other biomarkers such as neurofilaments. All data will be listed appropriately.

The B-cell counts, total IgG, total IgM, neurofilaments, lymphocytes and neutrophils will be summarized using descriptive statistics by visit-window. IgG, IgM, lymphocytes and neutrophils will also be summarized by visit-window and last prior DMT.

In addition, number and percentage of subjects with B-cells < the lower limit of normal (LLN) or < their baseline value (i.e., B-cell depleted) will be presented by visit window. For subjects who entered the safety follow-up, number and percentage of subjects with B-cell recovery (above LLN) will be summarized by SFU visit-window.

Number and percentage of subjects with IgG and IgM below LLN and meet the notable low level criteria in IgG or IgM by visit window will be provided. IgG and IgM will also be summarized by visit window and last prior DMT. A notably low IgG level is defined as a level that is ≤ 4.5 g/L (20% below LLN) and ≤ 0.36 g/L (10% below LLN) for IgM. LLN is 5.65 g/L for IgG and 0.4 g/L for IgM. For subjects who had IgG or IgM below LLN at the time of entering SFU, number and percentage of subjects with IgG or IgM recovery (above LLN) will be summarized by SFU visit-window.

Number and percentage of subjects with lymphocytes and neutrophils below LLN and meet the notable abnormalities by visit window will be provided. Lymphocytes and neutrophils will also be summarized by visit window and last prior DMT. Notable abnormalities for lymphocytes and neutrophils are listed in Table 2-12.

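### SAP 2.9.3.1 counts low IgG and IgM, and recovery from them, without reference to baseline, although subjects may enter the trial already below LLN

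*SAP*

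**What the plan says.** **Entry.** Exclusion criterion 17 (protocol 5.2) bars "Serum IgG < 500 mg/dL (according to central laboratory range". It gives no IgM value. The only other laboratory route to exclusion is "Any other clinically significant laboratory assessment as determined by the Investigator".

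**Thresholds.** SAP 2.9.3.1 states: "LLN is 5.65 g/L for IgG and 0.4 g/L for IgM". It adds: "A notably low IgG level is defined as a level that is ≤ 4.5 g/L (20% below LLN) and ≤ 0.36 g/L (10% below LLN", where the second figure is for IgM.

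**Low-value counts.** The same section plans the "Number and percentage of subjects with IgG and IgM below LLN and meet the notable low level criteria in IgG or IgM by visit window". Baseline plays no part in it.

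**Recovery.** The denominator is set by "For subjects who had IgG or IgM below LLN at the time of entering SFU", and the "number and percentage of subjects with IgG or IgM recovery (above LLN) will be summarized by SFU visit-window".

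**End of follow-up.** Protocol 9.2.1, for the visit six months after EOS, says: "If a subject has IgG and IgM results ≥ screening or LLN, this visit shall be considered final clinic visit for the subject". Footnote 6 of protocol Table 8-2 and SAP 2.1.2.2 use the same pair of references, screening value or LLN.

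**Elsewhere in the SAP.** SAP 2.9.3 counts CTC-graded abnormalities that are new or have worsened, and liver enzyme abnormalities that are newly occurring. SAP 2.9.3.1 defines B-cell depletion by LLN or the subject's own baseline.

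**The concern.** The trial has one arm, so the subject's own baseline is the only reference for what happens on drug. A count of subjects below LLN in an on-treatment window will be read as an on-drug finding, yet it can include subjects who were already there at screening. SAP 2.8 refers the secondary endpoint on abnormal laboratory results to SAP 2.9, where these counts sit. The split in SAP 2.9.4.3 (discontinuation or interruption by IgG below LLN at any time after baseline, repeated for IgM) has the same weakness, because a subject who was low at entry and stays low falls in the low group.

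The recovery row has a related problem. It asks every subject who enters SFU below LLN to rise above LLN, including those who were below it before treatment. For them, a full return to the starting point is tabulated as a failure to recover.

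**Working it through.** **Step 1: reproduce the SAP's own cut-offs.** IgG: 0.8 × 5.65 = 4.52 g/L, stated as 4.5 (20.4% below LLN, so rounding). IgM: 0.9 × 0.4 = 0.36 g/L, exact. The stated figures are sound.

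**Step 2: put the entry criterion in the same units.** 500 mg/dL × 10 / 1000 = 5.0 g/L. The gap to LLN is 5.65 − 5.0 = 0.65 g/L, or 0.65 / 5.65 = 11.5% of LLN. Subjects with IgG from 5.0 to just under 5.65 g/L are eligible and already below LLN.

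**Step 3: which low categories can exist before the first dose?**

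| | Entry limit | LLN | Notably low | Below LLN at entry? | Notably low at entry? |
|---|---|---|---|---|---|
| IgG | 5.0 g/L | 5.65 g/L | ≤ 4.5 g/L | Yes | No (5.0 > 4.5) |
| IgM | no numeric limit | 0.4 g/L | ≤ 0.36 g/L | Yes | Yes |

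**Step 4: apply the two follow-up criteria to one subject.** IgG is 5.3 g/L at screening, lower at SFU entry, and 5.3 again at the six-month visit. Protocol 9.2.1: 5.3 is at or above screening, so the IgG part of the criterion is met. SAP 2.9.3.1: 5.3 is not above 5.65, so the subject is not recovered. IgM of 0.35 g/L at screening and again at six months gives the same disagreement.

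**Step 5: how much of a low-value count could be pre-existing?** The documents give no rate of low immunoglobulin at baseline or on drug, so both are assumed. Let *b* be the share below LLN at baseline and *i* the share of the others who fall below it in a window, and suppose that those low at baseline stay low. Then:

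- share counted as low = *b* + (1 − *b*)*i*
- pre-existing part of that count = *b* / [*b* + (1 − *b*)*i*]

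For *b* = 5% and *i* = 10%: 0.05 + 0.95 × 0.10 = 14.5%, about 80 of 555 subjects, against 10% (about 53 subjects) among those normal at baseline. The pre-existing part is 0.05 / 0.145 = 34.5%.

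Pre-existing part of the low count over a wider range:

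| Low at baseline (*b*) | *i* = 5% | *i* = 10% | *i* = 20% |
|---|---|---|---|
| 1% | 16.8% | 9.2% | 4.8% |
| 5% | 51.3% | 34.5% | 20.8% |
| 10% | 69.0% | 52.6% | 35.7% |

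The result runs from minor to dominant, depending on a figure that the documents do not supply.

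**The case against.** The case for leaving the plan alone has substance. These are descriptive prevalence counts with no hypothesis test, and the SAP does not call them new or treatment-emergent. Baseline IgG and IgM are summarized, also by last prior DMT (SAP 2.3.3), and all values are listed. Protocol 12.5.2 plans shift tables from baseline to worst on-treatment value. Recovery above LLN is a stricter standard that also applies to B cells in the same section. Exclusion 7 (immunodeficiency) and investigator judgement under exclusion 17 may remove some subjects with low IgM.

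Most of this limits the point without removing it. A separate baseline table does not show which of the subjects low at Week 48 were low at screening. The itemised summaries in protocol 12.5.2 are for hematology and biochemistry, protocol Table 8-4 lists immunoglobulins apart from both, and SAP 2.9.3.1 specifies no immunoglobulin shift table. The list of changes in SAP section 4 is not visible, so one cannot say that such a table was dropped.

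Four stronger readings are tempting and should not be adopted:

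- A reader might infer that notably low IgG can also be pre-existing. It cannot on the qualifying value, since the entry limit of 5.0 g/L exceeds 4.5 g/L.
- A reader might infer that ending visits early removes later recoveries from the table. SAP Table 2-11 has only two SFU windows, ending at day 210, and protocol 9.2.1 applies its criterion at the visit that falls in the second.
- A reader might infer that the protocol declares these subjects recovered. Section 9.2.1 is a rule for ending visits and does not define a recovery outcome.
- A reader might turn the proportions in the working into a ceiling on the recovery percentage. The recovery denominator is only those who enter SFU below LLN. SFU is for subjects who stop early or do not continue ofatumumab, and nothing shows that they have the same mix of baseline-low and newly low subjects as all 555.

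**Conclusion.** The point holds as a gap in presentation. Eligibility and the SAP's LLN together allow subjects to be below LLN for IgG or IgM, or notably low for IgM only, before the first dose. SAP 2.9.3.1 then mixes these subjects with new cases, and its recovery definition counts a return to a low screening value as no recovery. The SAP takes baseline into account for graded laboratory tests and for B-cell depletion, and gives no reason for treating immunoglobulins differently.

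The size is unknown. Under the assumed inputs, the pre-existing part of a low-value count runs from 4.8% to 69.0%, and it would be negligible if almost no one enters low. No numerical effect on the recovery percentage can be derived from the documents. The primary analysis is not affected. This is a cheap improvement worth making in a single-arm safety report.

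**What to change.** In SAP 2.9.3.1:

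1. Present the below-LLN and notably-low counts by baseline status (at or above LLN, below LLN), or as a shift table from baseline to worst on-treatment value. Count new or worsening cases. Do not restrict the count to subjects who were normal at baseline: someone who enters with IgG of 5.2 g/L and falls to 4.4 g/L has become notably low on drug and must still be captured.
2. Report recovery in two rows: above LLN, as now, and at or above LLN or the subject's screening value, which matches the reference in protocol 9.2.1.
3. Use the same baseline split in the summary by IgG and IgM in SAP 2.9.4.3.

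Protocol Table 8-1 already schedules IgG and IgM at screening for every subject, so no new data are needed. The cost is a few more descriptive rows and some reprogramming. Eligibility and the rule for ending follow-up are untouched.

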2.9.4 Other safety data

2.9.4.1 ECG and cardiac imaging data

ECG data will be collected at baseline visit and EOS visit. Clinically significant findings from ECG evaluations will be reported as AEs and included in the analysis of AEs. ECG parameters include max heart rate, mean PR duration, mean QT duration, mean QRS duration, and QT corrected using Fridericia's correction formula (all as collected on the ECG CRF). Descriptive statistics of each ECG parameter will be provided for baseline and for the nominal visit (i.e., EOS visit). The number and percentage of subjects meeting the criteria defined in Table 2-13. Criteria for relevant ECG absolute or change from baseline values will be provided

for each criterion for baseline and for the nominal visit. A listing based on clinically significant findings will be provided.

Table 2-13 Criteria for relevant ECG absolute or change from baseline values

Absolute values criteria	Changes from baseline criteria	
Heart rate: HR <50 or HR > 120 beats/min	QRS complex : increase > 25% compared to baseline	
Pulse rate: PR <110 or PR >200 msec	QTcF > 500 msec and QTcF increase > 60 msec	
QRS complex: < 70 msec or > 120 msec		
QTcF < 350 or > 450 msec (males)		
QTcF <360 or > 460 msec (females)		

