8.4.2 Electrocardiogram (ECG)

An ECG will be performed and reviewed locally for the eligibility assessment at the Screening visit. Another ECG will be performed at the EOS visit. Additional unplanned ECGs may be performed at the Investigator's discretion if clinically indicated.

Single 12 lead ECGs are collected. The ECG should be recorded (after 10 minutes rest in the supine position to ensure a stable reading) according to the local site practice. Clinically significant ECG findings at Screening must be discussed with the Novartis Medical Advisor before administration of study drug.

The preferred sequence of cardiovascular data collection during study visits are ECG collection first, followed by vital signs and blood sampling. The Fridericia's QT correction formula (QTcF) should be used for clinical decisions.

The original ECGs on non-heat-sensitive paper (or a certified copy on non-heat-sensitive paper), appropriately signed must be collected and archived at the study site. Each ECG tracing must include study number, subject initials, subject number, date and time when ECG was performed, and filed in the study site source documents.

Findings and clinically significant abnormalities must be recorded on the relevant section of the medical history form and AE eCRF page as appropriate.

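### SAP Table 2-13 has no standalone QTcF change criterion, so a rise above 60 msec that ends at or below 500 msec is not counted as a rise

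*SAP*

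**What the plan says.** SAP 2.9.4.1 defines the ECG criteria in Table 2-13, which has one column for absolute values and one for changes from baseline.

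- **Absolute QTcF limits:** "QTcF < 350 or > 450 msec (males") and "QTcF <360 or > 460 msec (females").
- **QTcF change entry:** "QTcF > 500 msec and QTcF increase > 60 msec". This is the only QTcF entry in the change column.
- **The other change entry:** "QRS complex : increase > 25% compared to baseline", a change criterion with no absolute condition attached.

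The number and percentage of subjects meeting the criteria are given "for each criterion for baseline and for the nominal visit. A listing based on clinically significant findings will be provided". The other planned ECG outputs in that section are summary statistics ("Descriptive statistics of each ECG parameter will be provided for baseline and for the nominal visit (i.e., EOS visit") and adverse event reporting ("Clinically significant findings from ECG evaluations will be reported as AEs and included in the analysis of AEs").

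Protocol 8.4.2 schedules one ECG at Screening, and then "Another ECG will be performed at the EOS visit". Unplanned ECGs are allowed if clinically indicated, but SAP Table 2-1 limits the by-visit ECG summary to EOS data.

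**The concern.** A change-from-baseline column should show how many subjects shifted materially during the study. For QTcF, the printed entry counts a shift only when the final value also exceeds 500 msec. Smaller final values, however large the rise behind them, are left out of the change count.

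No other planned summary fills the gap. SAP 2.9.3 (laboratory data) and 2.9.4.2 (vital signs) both specify change-from-baseline summaries. For ECG parameters, 2.9.4.1 specifies descriptive statistics at baseline and at EOS, with no summary of the within-subject difference. The change column of Table 2-13 is therefore the only place where a subject's two QTcF values are compared.

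What is at stake is interpretation. If the joint row shows zero, a reader of the study report could take it to mean that no QTcF rise above 60 msec occurred. The row cannot support that conclusion.

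**Working it through.** The plan states no figure to reproduce here. The check is one of logic between thresholds.

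**Inputs (all from SAP Table 2-13).** Let b be baseline QTcF and e be EOS QTcF, in msec.

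- Absolute flag, men: e < 350 or e > 450.
- Absolute flag, women: e < 360 or e > 460.
- Change flag, as printed: e > 500 and e − b > 60.

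**Step 1: what the change flag adds.** Since 500 > 450 and 500 > 460, any e above 500 already breaches the upper absolute limit for either sex. The change flag therefore marks a subgroup of subjects who already carry an absolute flag, and it adds no further subject.

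**Step 2: where a rise above 60 msec can end.**

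| EOS value | Example | Absolute flag | Change flag |
|---|---|---|---|
| Within the sex limits | Man, 370 to 445 (+75) | No | No |
| Within the sex limits | Woman, 380 to 455 (+75) | No | No |
| Above the limit, at or below 500 | Man, 390 to 470 (+80) | Yes | No |
| Above 500 | Man, 420 to 510 (+90) | Yes | Yes |

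Only the last row is recorded as a rise. The man ending at 470 is counted at EOS in the same way as a man who was at 470 on both occasions.

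**Step 3: can this happen from a baseline inside the limits?** The absolute range is 450 − 350 = 100 msec wide for men and 460 − 360 = 100 msec wide for women. A rise above 60 msec therefore fits inside it.

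**Step 4: exhaustive check.** All integer pairs (b, e) from 300 to 600 msec were run through the printed rules.

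| Pairs | Men | Women |
|---|---|---|
| Meeting the change flag | 19,050 | 19,050 |
| … of which not already flagged by the absolute limits | 0 | 0 |
| Rise > 60, ending inside the limits | 4,095 | 5,050 |
| … of which baseline also inside the limits | 820 | 820 |
| … of which change flag met | 0 | 0 |
| Rise > 60, ending above the limit and at or below 500 | 5,775 | 4,820 |
| … of which change flag met | 0 | 0 |

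These counts show that the gap exists for both sexes. They are grid points, not expected numbers of patients.

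**The case against.** Five points can be made for the plan.

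1. **A nested row is not a fault in itself.** The SAP nests severity tiers elsewhere: SAP 2.9.3.1 counts IgG below the lower limit of normal (5.65 g/L) and then a notably low level (4.5 g/L or less). The joint QTcF row also does something the absolute rows cannot: it separates a value above 500 msec reached by a large on-study rise from one that was already high. This stands. A reader might infer from Step 1 that the row is redundant or mistaken, but the documents do not support that. The gap is the missing standalone row.

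2. **The subjects are not invisible.** A reader might infer that such a rise appears nowhere. That goes too far. These subjects contribute to the descriptive ECG statistics, and a finding judged clinically significant is reported as an AE and listed. This stands too, but both of those routes depend on clinical judgement and neither is a programmed count of rises.

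3. **The word *and* may have been meant to list two criteria.** This cannot be excluded, and on that reading the gap closes. Against it, the same table uses *or* wherever it offers alternatives, so a programmer following the text would code a conjunction. Either way the cell needs clarifying.

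4. **The consequence is small.** The secondary abnormality endpoint covers laboratory and vital sign results, not ECG. Protocol 12.5.2 specifies no ECG analysis. The two scheduled tracings are single 12-lead recordings almost two years apart, with no control arm, so a count of rises could hardly be attributed to the drug. This stands and limits the priority.

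5. **The choice of rows is partly preference.** Nothing in the documents requires either threshold to be tabulated alone. That is true, but both thresholds are the SAP's own, and the section sets out to report changes from baseline.

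**Conclusion.** The point holds for the counts in Table 2-13 as printed. There is no standalone QTcF change criterion. A rise above 60 msec ending at or below 450 msec (men) or 460 msec (women) meets no upper-limit or change criterion for QTcF, and one ending between those limits and 500 msec is recorded only as an absolute abnormality.

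The conclusion rests on reading *and* as a conjunction. The set logic itself needs no further assumption. The number of subjects affected cannot be given, because the documents contain no QTcF distribution. A reader might infer that a QTcF signal has been missed or hidden, but nothing in the documents shows that any subject had such a rise.

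This is a low-priority improvement to descriptive safety reporting. It does not touch the primary analysis, the secondary endpoints or any clinical rule.

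**What to change.** In SAP Table 2-13:

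- Add an increase in QTcF from baseline above 60 msec as its own row in the change column.
- Add QTcF above 500 msec as its own row in the absolute column.
- Keep the joint row, if wanted, as a severity tier.
- If the existing entry was meant as two criteria, print it as two rows.

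The cost is one or two extra descriptive rows in one table, using thresholds the SAP already names and ECG data already collected. No extra assessment is needed.
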